3.2.3 Choice of study population

FPG and HbA1c

The upper limit for fasting plasma glucose (FPG) and HbA1c at enrolment, $FPG \leq 180$ mg/dL, and $HbA1c \leq 8.5$ % was chosen to select a patient population with diabetes without risking the patient's health due to sustained hyperglycaemia.

Pregnancy or breastfeeding

Dapagliflozin has not been tested in pregnant women and the risks to embryo, foetus, and infant are unknown. For this reason, women who are pregnant or breastfeeding are excluded and women of child-bearing age are instructed to take precautions to avoid becoming pregnant during the study.

Other

The purpose of the majority of the inclusion and exclusion criteria is to limit confounding factors that may complicate the interpretation of the study results or to exclude patients whose safety could be compromised by participation in the study.

3.2.4 Choice of dose

[Dapagliflozin]

In the ongoing dose-finding study in Japanese patients with type 2 diabetes (D1692C00005), the doses, 1, 2.5, 5 and 10 mg were chosen. In the overseas studies, 2.5, 5 and 10 mg are included in the Phase III development programme with double-blind controlled studies with duration of up to 2 years.

The dose of 10 mg was chosen for this study as the expected highest dose for type 2 diabetes patients.

[Voglibose]

The dose of voglibose used in the study, 0.2 mg tid, is a commonly used dose in clinical practice. To allow reliable evaluation of the effect on the pharmacokinetics of dapagliflozin, it is important that the patients are on a stable dose of voglibose.

4. SUBJECT SELECTION CRITERIA

Investigator(s) should keep a record, the subject screening log, of subjects who entered pre-study screening.

Each subject must meet all of the inclusion criteria and none of the exclusion criteria for this study. Under no circumstances can there be exceptions to this rule.

4.1 Inclusion criteria

For inclusion in the study subjects must fulfil the following criteria:

1. Provision of informed consent prior to any study specific procedures
2. Male or female who are ≥ 20 years of age
3. Women of child-bearing potential who comply with the following:
 - Use an adequate method of contraception to avoid pregnancy throughout the study and for up to 4 weeks after the study
 - Have a negative urine pregnancy test at Visit 1
4. Diagnosed with type 2 diabetes
5. Already on voglibose treatment with a steady dosage for at least 8 weeks (one change in voglibose dose to 0.2 mg tid by 4 weeks before is allowable)
6. Fasting C-peptide > 1.0 ng/mL (0.33 nmol/L)
7. FPG ≤ 180 mg/dL
8. HbA1c $\leq 8.5\%$

4.2 Exclusion criteria

Subjects must not enter the study if any of the following exclusion criteria are fulfilled:

Endocrine and metabolic disorders

1. Diagnosis of Type 1 diabetes mellitus, known diagnosis of MODY or secondary diabetes mellitus
2. History of diabetic ketoacidosis
3. Symptoms of poorly controlled diabetes including, but not limited to, marked polyuria, polydipsia, and/or greater than 10% weight loss during the 3 months prior to enrolment

4. History of bariatric surgery (ie, any surgery to treat obesity; for example, gastric banding or procedures that involve bypassing or transposing sections of the small intestine). History of liposuction is allowed.
5. Diabetes insipidus
6. Thyroid-stimulating hormone (TSH) values outside normal range

Kidney disorders

7. Calculated Creatinine Clearance <50 mL/min (calculated by Cockcroft-Gault formula)
8. Urine albumin: creatinine ratio (UACR) >1800 mg/g (>203.4 mg/mmol)
9. History of unstable or rapidly progressing kidney disease
10. Known condition of familial renal glucosuria

Hepatic disorders

11. Severe hepatic insufficiency and/or significant abnormal liver function defined as aspartate aminotransferase (AST) >3X upper limit of normal (ULN) and/or alanine aminotransferase (ALT) >3X ULN
12. Total bilirubin >2.0 mg/dL (>34.2 µmol/L)
13. Positive serologic evidence of current infectious liver disease including Hepatitis B viral antibody IgM, Hepatitis B surface antigen and Hepatitis C virus antibody
14. History of drug-induced liver enzyme elevations
15. History of severe hepatobiliary disease or hepatotoxicity with any medication

Cardiovascular disorders

16. Congestive heart failure defined as New York Heart Association (NYHA) class III and IV, unstable or acute congestive heart failure. Note: eligible patients with congestive heart failure should have careful monitoring of their volume status throughout the study.
17. Significant cardiovascular history within the past 6 months prior to the screening visit, defined as: myocardial infarction, unstable angina pectoris, transient ischemic attack, unstable or previously undiagnosed arrhythmia, cardiac surgery or revascularization (coronary angioplasty or bypass grafts), or cerebrovascular accident. In addition, patients who have unstable cardiovascular disease at enrolment in the judgment of the investigator are excluded from the study.
18. Systolic BP \geq 170 mmHg and/or diastolic BP \geq 100 mmHg as an average value

Hematologic/oncologic disorders/conditions

19. Haemoglobin ≤ 10 g/dL (≤ 100 g/L) for men; haemoglobin ≤ 9.0 g/dL (≤ 90 g/L) for women
20. History of chronic haemolytic anaemia or haemoglobinopathies (for example, sickle cell anaemia, thalassemia, sideroblastic anaemia)
21. Donation or transfusion of blood, plasma, or platelets within the past 3 months prior to Visit 1
22. History of malignancy within the last 5 years, excluding successful treatment of basal or squamous cell skin carcinoma

Infectious disease/immunologic disorders

23. Known immunocompromised status, including patients who have undergone organ transplantation

Musculoskeletal disorders

24. Creatine Kinase (CK) $> 3X$ ULN
25. History of drug-induced myopathy or drug-induced CK elevation

Reproductive status

26. Pregnant or breastfeeding patients

Prohibited medications

27. Treatment combination for diabetes within 12 weeks of Visit 1, except the minimum approved doses of one antidiabetes drug with voglibose
28. Use of insulin within 24 weeks of Visit 1 (with the exception of one temporary period of daily insulin injections no later than 2 weeks prior to the study)
29. Treatment with glucocorticoids equivalent to oral prednisolone ≥ 10 mg betametasone ≥ 1.2 mg, dexamethasone ≥ 1.5 mg, hydrocortisone ≥ 40 mg) per day within 30 days prior to Visit 1; topical or inhaled corticosteroids are allowed
30. Use of concomitant medication after Visit 1, except voglibose, antihypertensives (other than diuretics and those which may affect the pharmacokinetics of dapagliflozin), statins, warfarin-type anticoagulants and low dose aspirin

Other

31. Any clinically significant abnormality identified on physical examination, ECG or laboratory tests, which in the judgement of the investigator would compromise the patient's safety or successful participation in the clinical study

32. Patients who, in the judgement of the investigator, may be at risk for dehydration
33. Acute or chronic metabolic acidosis
34. History of alcohol abuse or illegal drug use within the past 12 months
35. Involvement in the planning and conduct of the study (applies to both AstraZeneca and Bristol-Myers Squibb staff or staff at the study centre)
36. Previous enrolment or randomisation to treatment in the present study
37. Previous participation in a clinical study with dapagliflozin in which the patient received at least one dose of study medication.
38. Participation in another clinical study during the last 1 month

Procedures for withdrawal of incorrectly enrolled subjects see Section [5.3](#).

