3.1 Overall study design and flow chart

This is an open-label, multi-centre drug-drug interaction study to assess the effect of voglibose 0.2 mg tid on the pharmacokinetics (PK), safety and tolerability of dapagliflozin when a single oral dose of dapagliflozin 10 mg is administered to Japanese patients with type 2 diabetes mellitus (T2DM) treated with voglibose.

In this study 22 Japanese patients with T2DM will be assigned to treatment. The patients should be on stable treatment with voglibose at least 8 weeks before enrolment (one change in voglibose dose to 0.2 mg tid by 4 weeks before enrolment is allowed).

The study consists of two PK sampling periods: period I of a single dose of dapagliflozin with voglibose and period II of a single dose of dapagliflozin alone. The PK sampling periods will be separated by a wash-out period of 7(+7) days between the last blood sampling in period I and the dose of dapagliflozin in period II.

In period I, each patient will take a single oral dose of 10 mg dapagliflozin (Visit 2) together with voglibose and plasma samples will be collected through Visit 4 (up to 72 hours = 3 days after dose) for PK assessment. In period II, after the wash-out period, a single oral dose of 10 mg dapagliflozin will be administered without voglibose. Plasma samples will be collected through Visit 7 (up to 72 hours = 3 days after dose) for PK assessment.

The patients will take voglibose just before each meal (tid) until and including Study day 3 (Visit 4). The patients will stop taking voglibose on Study day 4 and no voglibose will be taken until after the last blood sampling for PK assessment on Study day 14 (Visit 7).

multiple ascending dose study (MB102025) was 1.5 times higher than healthy subjects) and the possible extension by interaction with voglibose, it is necessary to draw blood samples until 72 hours after dapagliflozin dosing. A wash-out period of 7 (+7) days between PK sampling periods is considered necessary in order for dapagliflozin and voglibose to be eliminated to remove carry-over effect. As study design, only single sequence fashion (combination followed by dapagliflozin mono-therapy) is adopted in terms of operational feasibility since it takes at least 4 weeks for voglibose to stabilize gastrointestinal condition and adverse events.

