5.6 Concomitant and post-study treatment(s)

No concomitant medication or therapy will be allowed except for antihypertensives (other than diuretics and those which may affect the pharmacokinetics of dapagliflozin), statins, warfarin-type anticoagulants and low dose aspirin (≤ 100 mg). If these allowed medications are used they must be administered on a fixed daily dose throughout the study period.

During the wash-out period, concomitant drugs (except antidiabetic agents and glucocorticoids) can be used if medically needed, under the condition that Visit 5 (2nd dapagliflozin administration) will be conducted ≥ 7 days after the last dose of the concomitant drugs.

During the PK sampling periods (Visits 2 to 4 and Visits 5 to 7), a change of concomitant medications (change of the dose and addition of a new drug) is not be allowed basically, but if it is acutely necessary, the investigators should consult with AstraZeneca.

Other medication, which is considered necessary for the subject's safety and well being, may be given at the discretion of the investigator and recorded in the appropriate sections of the Case Report Form.

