6.2.1 Medical examination and demographic measurements

Enrolment medical examination and demographic measurements

Each patient will undergo an enrolment medical examination (Visit 1) 7 (± 3) days prior to Visit 2. Data to be collected are as follows:

- Recording of demographic data - date of birth, sex, race
- Diabetes History
- Medical/Surgical history, past and current
- Concomitant medication
- A blood sample for standard clinical chemistry and haematology assessments and spot urine sample for urinalysis
- A resting blood pressure and pulse rate measurement
- Urine pregnancy test (only for pre-menopausal women of child-bearing potential). In the event of suspected pregnancy during the study, the test should be repeated.
- Weight (to be recorded in kilograms to one decimal place)

Data listed above are to be recorded at Visit 1. Patients will also be given diet and life-style advice at Visit 1.

Measurements at Visit 2

The following measurements will be performed and recorded only at Visit 2.

- Height (to be recorded in centimetres)

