12.1.1 PK analysis set

All subjects who received at least one dose of investigational product and whose PK data are available without the protocol violations or deviations relating to inclusion/exclusion criteria, PK sampling and concomitant medications will be included in the PK analysis set.

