12.2.3 PK parameter

All PK parameter will be listed by subject and summarised by the dosing condition.

All PK parameters, except for t_{\max} , will be summarised using the following descriptive statistics.

- Number of subjects
- Geometric mean
- CV
- Arithmetic mean
- SD
- Minimum
- Median
- Maximum

For t_{\max} , the following descriptive statistics will be presented.

- Number of subjects

- Minimum
- Median
- Maximum

The comparison between dosing condition for each PK parameters will be made based on complete case analysis. The pharmacokinetic variables AUC and C_{\max} will be log-transformed before analysis. To assess the effect of voglibose on the AUC and C_{\max} of dapagliflozin, they will be analysed using a mixed effect ANOVA model including the dosing condition (with voglibose or without voglibose) as fixed effect and patient as a random effect. Estimates and confidence intervals of the difference between the dosing conditions will first be constructed in the log scale. Then the estimates and confidence intervals of ratio of geometric means between the dosing conditions in the original scale will be obtained by taking anti-logarithms. The estimates and 2-sided 90% confidence intervals of the ratio of geometric means will be presented for:

- AUC (with voglibose) / AUC (without voglibose)
- C_{\max} (with voglibose) / C_{\max} (without voglibose)

It will be concluded that there is no pharmacokinetic drug-drug interaction if the confidence interval falls within 0.8 – 1.25 for AUC and C_{\max} of dapagliflozin. No adjustment for the multiplicity will be made.

The comparison between the dosing conditions for other PK parameters will be made in descriptive manner.

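### Unlisted drugs may be taken up to 4 days before the first dapagliflozin dose but must stop at least 7 days before the second, so in a fixed sequence the shorter gap can fall only on the with-voglibose dose

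*Protocol*

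**What the plan says.** Before the first dose, exclusion 30 (section 4.2) bars "Use of concomitant medication after Visit 1, except voglibose, antihypertensives" of most kinds, statins, warfarin-type anticoagulants and low-dose aspirin. Use up to Visit 1 is not barred. Only insulin, higher-dose glucocorticoids and participation in another trial have an earlier cut-off (exclusions 28, 29 and 38).

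Section 6.2.1 sets the timing: "Each patient will undergo an enrolment medical examination (Visit 1") 7 (±3) days before Visit 2, the day of the first dapagliflozin dose.

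For the second dose, section 5.6 states: "During the wash-out period, concomitant drugs (except antidiabetic agents and glucocorticoids) can be used if medically needed", provided that Visit 5 is at least 7 "days after the last dose of the concomitant drugs". It gives no such interval before Visit 2.

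Exclusion 27 bars combination treatment for diabetes in the 12 weeks before Visit 1, "except the minimum approved doses of one antidiabetes drug with voglibose". Neither exclusion 30 nor section 5.6 lists that second drug among those that may continue.

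The rationale for the study period says that "only single sequence fashion (combination followed by dapagliflozin mono-therapy) is adopted in terms of operational feasibility". The primary model in section 12.2.3 is a mixed ANOVA "including the dosing condition (with voglibose or without voglibose) as fixed effect and patient as a random effect". The PK analysis set (section 12.1.1) keeps patients with PK data "without the protocol violations or deviations relating to inclusion/exclusion criteria, PK sampling and concomitant medications".

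**The concern.** The primary result is a within-patient comparison of two single doses of dapagliflozin. Conditions other than voglibose should therefore be as alike as possible before each dose. The protocol sets a minimum drug-free interval of 7 days before the dose without voglibose, but allows 4 days before the dose with it.

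In a two-sequence crossover, such a difference would be spread over both conditions. Here every patient takes the combination first, so period and dosing condition coincide and no term in the model can separate them. If a drug stopped at Visit 1 still affects dapagliflozin at the first dose but no longer at the second, the change in AUC or Cmax is attributed to voglibose. It could push the 90% interval outside 0.8 to 1.25, or offset a true interaction. The patient has broken no rule, so section 12.1.1 does not remove the pair. An analysis plan cannot restore a drug-free interval after dosing, so the eligibility and scheduling text has to secure it.

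**Working it through.** **Plan's own figure.** Section 12.3 gives within-subject SDs of 0.095 (log AUC) and 0.2024 (log Cmax), 20 patients, limits 0.8 to 1.25 and true ratio 1. The standard error is SD × √(2/20), which is 0.0300 for AUC and 0.0640 for Cmax. With 19 degrees of freedom and 5% on each side, the exact power is above 99.9% for AUC and 91.3% for Cmax. Both agree with the stated values (over 99% and 90%).

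**Drug-free interval.** Take Visit 2 as day 0.
- Visit 1 lies between day −(7+3) = −10 and day −(7−3) = −4.
- Visit 7 is study day 14, 3 days after Visit 5, so Visit 5 is day 11, or up to day 18 with the +7 allowance.
- A drug last taken at Visit 1 is 4 to 10 days out at dose 1. At dose 2 it is 4+11 = 15 to 10+18 = 28 days out.
- The minimum in section 5.6 before dose 2 is 7 days, so the shortfall before dose 1 is at most 7−4 = 3 days. It occurs on three of the seven permitted Visit 1 days (4, 5 or 6 days before Visit 2).

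**Residual drug.** The protocol gives no half-life, so these are assumed. Share remaining = 2^(−days/half-life).

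| Half-life | 4 days | 7 days | 15 days |
|---|---|---|---|
| 1 day | 6.3% | 0.8% | 0.003% |
| 2 days | 25.0% | 8.8% | 0.6% |
| 3 days | 39.7% | 19.8% | 3.1% |

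Moving from 4 to 7 days removes a fraction 1 − 2^(−3/half-life) of what remains: 87.5%, 65% or 50%.

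**What a residual effect would do to the result.** The protocol gives no effect size, so these are illustrations. If a share f of pairs has its period I value multiplied by r, the observed ratio is the true ratio × r^f. The SDs are kept as in section 12.3.

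| r | f | Ratio | Cmax power |
|---|---|---|---|
| 0.9 | 10% | 0.990 | 90.9% |
| 0.9 | 25% | 0.974 | 88.9% |
| 0.8 | 10% | 0.978 | 89.6% |
| 0.8 | 25% | 0.946 | 80.4% |

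AUC power stays above 99% in all four cases. In the other direction, take a true AUC ratio of 0.80 and r = 1.1. The chance of concluding no interaction rises from 5% to 9% (f = 10%, ratio 0.808) or 19% (f = 25%, ratio 0.819).

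These figures show the total effect of a residual, not the part due to having 4 rather than 7 days. They are also not derived from the half-life table: nothing in the protocol links a given residual to a 10% or 20% change in dapagliflozin exposure.

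**The case against.** The 7 days in section 5.6 is a condition on an allowance, namely drugs taken for medical need between the two doses. A reader might infer that it is the protocol's general drug-free standard before any dapagliflozin dose, and that exclusion 30 breaks it. The text does not say that. Before dose 1 there is a separate control, a ban from Visit 1, and on the nominal schedule Visit 1 is 7 days before Visit 2, so the two intervals match. This stands: the mismatch lies at the edge of a visit window.

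A reader might also infer from exclusion 27 that patients stopping a second antidiabetes drug at Visit 1 are to be expected. That criterion is a 12-week look-back. It allows such a drug but does not require it to continue to Visit 1, and it may have ended weeks earlier. This stands too. The listed drugs that may continue are held at a fixed daily dose, so they are balanced across the two doses.

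The illustrations need many affected patients. If Visit 1 falls evenly over the seven permitted days, then for shortfall pairs to make up 10% or 25% of the total, about 0.10/(3/7) = 23% or 0.25/(3/7) = 58% of patients would have to stop an unlisted drug at Visit 1. The 9% and 19% figures also assume a true AUC ratio of exactly 0.80, although section 1.3 describes voglibose as not absorbed. These figures therefore cannot be read as the expected cost of the defect.

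Finally, a 7-day minimum leaves part of the asymmetry in place, because the single sequence remains, and the protocol discloses and justifies that choice. This limits what the fix achieves, but is no reason to keep the shorter interval. The study plan table is not in the text at hand, so a note there on medication timing could not be checked.

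**Conclusion.** The point holds as a small, avoidable asymmetry. Under exclusion 30 and section 6.2.1 the minimum drug-free interval is 4 days before the with-voglibose dose; under section 5.6 it is 7 days for a drug used before the dose without voglibose. The shortfall is up to 3 days, on three of seven permitted visit days, and only for a patient who takes an unlisted drug until Visit 1. With one sequence and no period term, any residual effect would be read as a voglibose effect, and the compliant patient would stay in the PK analysis set.

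The conclusion rests on date arithmetic and on reading exclusion 30 as governing the time before the first dose, with section 5.6 governing afterwards. On that reading, wash-out use that meets the 7-day condition is not a breach of exclusion 30, so the lack of a cross-reference between the two is no defect. How many patients are affected, and by how much, is unknown and may be zero. The stated sample size and power are correct for their assumptions. The change is worth making because it costs almost nothing, not because a loss of power or a false conclusion has been shown.

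**What to change.** Reword exclusion 30 to bar concomitant medication outside the present list after Visit 1 or within 7 days before the first dapagliflozin dose. In section 6.2.1, add that for a patient who stops such a drug at Visit 1, Visit 2 takes place 7 to 10 days after the last intake. This lies inside the existing 7 (±3) day window and gives both doses the same 7-day minimum.

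It reduces the difference in time since last intake but does not eliminate it. Such a drug would still be 7 to 10 days out at dose 1, against at least 7+11 = 18 days at dose 2, and for an assumed 3-day half-life 19.8% would still remain at 7 days.

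The cost is one reworded criterion and one added sentence, with no extra visit, sample or patient. Patients who stop a drug at Visit 1 lose the three shortest intervals of the window (4, 5 and 6 days).

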5. STUDY CONDUCT

5.1 Restrictions during the study

Patients will be required to:

1. Abstain from food from 22:00 and from beverages (except water) from 24:00 the night before each visit. Water will not be allowed for 2 hours before each administration of dapagliflozin.
2. Abstain from tobacco/nicotine use from 12 hours prior to each visit and from alcohol intake 24 hours prior to each visit.
3. Abstain from donating blood during the study and for 3 months after the last study day.

5.2 Subject enrolment and randomisation

The Principal Investigator will:

1. Obtain signed informed consent from the potential subject before any study specific procedures are performed.
2. Assign potential subject a unique enrolment number, beginning with 'E#'.
3. Determine subject eligibility. See Sections [4.1](#) and [4.2](#)
4. Assign eligible subject the unique subject number

If a subject withdraws from participation in the study, then his/her enrolment code/the unique subject number cannot be reused.

